4.1.1 Precision of Estimates of Secondary Endpoints

There is no longitudinal data on our secondary endpoints so it is not possible to provide precision estimates for those outcomes for which change from baseline will be analyzed. However, data are available for cross-sectional means and standard deviations for our secondary endpoints. Table 3.4 provides estimates of the precision of estimates of the means for each secondary endpoint based on half the width of a 95% confidence interval (approximately 0.4 standard deviations). That is, we can say with 95% confidence that the true value of the parameter will be no further from the observed estimate than the value reported as the precision estimate.

Statistical Analysis Plan

Table 4.4 Estimated Precision for QOL Outcomes

Outcome Category	Outcome	Mean	Standard Deviation	Precision
Metabolic	HbA1c	6	0.7	0.28
	c-Peptide	2	0.7	0.28
	MMTT	133	55	22
	Hypo Score	850	750	300
	MAGE	8	4	1.6
	LI	223	200	80
SF-36 Health Survey	Physical Functioning	96	6	2.4
	Role-Limitations Physical	83	22	8.8
	Role-Limitations Emotional	82	18	7.2
	Bodily Pain	74	14	5.6
	Social Functioning	84	15	6.0
	Vitality	54	17	6.8
	Mental Health	60	13	5.2
	General Health	75	16	6.4

Statistical Analysis Plan

Outcome Category	Outcome	Mean	Standard Deviation	Precision
	Physical Component Summary	56	5	2.0
	Mental Component Summary	43	8	3.2
EQ-5D(VAS)		83	13	5.2
Hypoglycemia Fear Survey	Behavior	6	11	4.4
	Worry	5	12	4.8
Diabetes Distress Scale	Emotional Burden	24	25	10
	Physician-Related Distress	0	0	
	Regimen-Related Distress	14	22	8.8

5. General Analysis Definitions

5.1 *Study Period and Visit Window Definition*

5.1.1 Study Period

The trial consists of three periods: (1) the pre-transplant period, which includes screening, enrollment, and wait list time; (2) the period that includes the islet transplant procedure(s); and (3) follow-up visits through 24 months following the last transplant. The study period of this trial is a 36-month follow-up after the final islet transplant. Subjects may undergo up to 3 transplants in the course of this study; the last transplant can occur not later than 8 months following the first transplant.

In the first period, individuals who meet the general inclusion criteria will be approached regarding participation in the study. After informed consent has been obtained, they will be formally enrolled into the study. Eligibility will be confirmed based on the results of the screening visit procedure detailed in Appendix 1 of the CIT-06 protocol. Enrolled subjects who meet the eligibility screening for the studies will be put on the waiting list for an islet transplant.

After completion of the screening assessments confirming eligibility for the study, a subject will undergo 12 months of intensive insulin therapy (IIT) by an experienced diabetologist (see Appendix 3). If a subject received at least 12 months of **intensive diabetes management** prior to enrollment and experienced at least one episode of **severe hypoglycemia** during that time, the subject would not be required to receive IIT while on study as long as they have a Clarke score of 4 or more. A subject is required to return to the study site for clinic visits every 3 months while undergoing IIT and while on the waitlist. Monthly HbA1c sampling between the required 3 month interval visits may be drawn locally, sent from the local lab to the study site and then shipped to the central lab for testing. Eligibility will be reconfirmed after 4 months of IIT and after 12 months of IIT. All eligibility assessments must be within the windows required for initial study enrollment. Once eligibility has been reconfirmed, a subject will be placed on the **wait list**. The subject will continue IIT while on the **wait list**.

Once a compatible islet preparation becomes available, a subject's eligibility will be re-confirmed and eligible subjects will begin immunosuppression therapy on Day -2 (Day 0 is defined as the day of transplant).

During the post-transplant follow-up period, subjects may receive up to two additional transplants. After receiving his/her first islet transplant, if a subject does not meet the criteria for insulin independence described in Study Definitions in the CIT-06 protocol, but has either a basal or stimulated C-peptide level ≥ 0.3 ng/mL (0.1 nmol/L), s/he will be considered for a second islet transplant. A subject who does not meet this criterion will be considered a transplant failure. A second islet transplant will be considered at 30 days but before 8 months after the first islet transplant and when all required metabolic assessments are complete. If, after the second islet transplant, both basal and stimulated C-peptide levels remain <0.3 ng/mL (0.1 nmol/L), the

Statistical Analysis Plan

recipient will be considered to have failed the endpoint, and immunosuppression will be managed as described in the protocol. A third islet transplant will be considered only if all the criteria described in Section 7.6 of the CIT-06 protocol are met. Islet transplant recipients who have completed 8 months of follow up after their first infusion will no longer be eligible for additional islet transplants under the CIT-06 protocol.

5.1.2 Visit Windows

The number of visits that occur before the first islet transplant will be determined by time on the waiting list and cannot be determined in advance. Screening tests and baseline measurements that are obtained during this period must be obtained within specified windows relative to the day induction immunosuppression is initiated, as described in Appendix 1 of the CIT-06 protocol (section 7). Following each transplant, up to 23 visits may be scheduled. Subsequent transplants restart the clock at day 0. Table 4.1 describes all visits, their scheduled times relative to the islet transplant, and the allowable visit windows.

Table 4.1 - Study assessment time points and visit windows

Time Points (days relative to transplant)	Visit Number	Visit Window (days around target)	Equivalent (weeks or months)
Screening	01	N/A	N/A
IIT \geq 12 months	02		
Waitlist/Baseline	03	N/A	N/A
Baseline	04		
0	05	N/A	N/A
3	06	N/A	N/A
7	07	± 3	W1
14	08	± 3	W2
21	09	± 3	W3
28	10	± 3	W4
56	11	± 7	M2

Statistical Analysis Plan

Time Points (days relative to transplant)	Visit Number	Visit Window (days around target)	Equivalent (weeks or months)
75	12	±5	M2.5
180	13	±7	M6
270	14	±14	M9
365 after most recent transplant	15	±14	M12
Y1 365 days after first transplant	Y1	±14	M9
M 15	16	±14	M15
M 18	17	±14	M18
M 21	18	±14	M21
M24 after most recent transplant	19	±14	M24
Y2 730 days after first transplant	Y 2	±90	Y2 After first transplant
M27	20	±14	M27
M30	21	±14	M30
M33	22	±14	M33
M36 after most recent transplant	23	±14	M36
Y3 1095 days after first transplant	Y 3	±90	Y3 After first transplant

Statistical Analysis Plan

This follow-up schedule will restart with visit 05 on the day that a subsequent islet transplant is performed. Yearly visits occur after the first transplant. The detailed activities for each scheduled follow-up visit are described in Appendix 1 of the CIT-06 protocol.

5.2 Study Populations

The study population consists of individuals with T1D who have had a kidney transplant and who meet the eligibility criteria for the trial described in Section 3 of the CIT-06 protocol. This section of the SAP describes three study populations. All efficacy analyses will be done on the ITT population. Parallel analyses will be done on the per-protocol population. Safety analyses will focus on the safety population.

5.2.1 Intent-to-Treat Population

All efficacy and safety analyses will be based on a modified ITT principle: any subject in whom protocol-directed therapy (*e.g.*, induction immunosuppression) is initiated will be included in the ITT population. Subjects who are transplant eligible but for whom a protocol directed therapy is not initiated will be listed in the final study report but will not be included in the ITT population.

A subject who is transplant eligible but never receives protocol-directed therapy will not be included in the analysis.

5.2.2 Per-Protocol Population

A per-protocol analysis will include all subjects in whom the islet transplant procedure is initiated. The procedure will be considered initiated when the operator (*e.g.*, surgeon or interventional radiologist) has started the process of obtaining access to the portal vein (*i.e.*, entered the body with a needle or scalpel).

5.2.3 Safety Population

The safety population consists of any subject in whom protocol-directed therapy (*e.g.*, induction immunosuppression) is initiated. Subjects in this population might not receive an islet transplant.

5.3 Treatment Assignment and Treatment Groups

5.3.1 Treatment Assignment

This is a single-arm study. All eligible subjects for whom an acceptable isolation is identified will receive at least one islet transplant. Enrolled subjects who meet the eligibility criteria will be placed on a waiting list for a transplant. Once a compatible pancreas becomes available, the subject will be reevaluated to ensure that s/he satisfies all inclusion/exclusion criteria and therefore is still eligible for CIT-06.

Statistical Analysis Plan

5.3.2 Treatment Groups

The treatment in CIT-06 is the islet transplant and its associated immunosuppression. This is a single arm, open label trial and everyone receives the same study treatment.

5.3.3 Center Pooling Method

The primary analysis assumes no between-center variability with regard to the favorable outcome resulting from the treatment. The data from all centers will be pooled without any adjustment for centers.

6. Subject Disposition

The number of subjects enrolled and treated will be summarized and reported in the following categories:

- The numbers of subjects who are screened - total and grouped by center.
- The numbers of subjects who are excluded from study participation - total and grouped by center. The numbers will also be tabulated by the reason for exclusion.
- The numbers of subjects who are enrolled (sign informed consent for screening) - total and grouped by center.
- The numbers of subjects who are eligible for the transplant both after the enrollment and completion of IIT and before the transplant, grouped by center.
- The numbers of subjects who are lost to follow-up, grouped by center and reason. (The rules for premature termination of study treatment are fully described in Section 5.7.3 of the CIT-06 protocol).

A list of all enrolled subjects (grouped by center) who are prematurely terminated from the study (withdraw consent or are lost to follow-up) will be provided. The list will give subject identification, the specific reason for termination, immunosuppression regimen and the duration of treatment before the termination.

7. Protocol Deviations

Major protocol deviations will be summarized by center and for the total study and grouped into the following categories:

- Impacts the inclusion and/or exclusion criteria (PD1)
- Involves consent violations (PD2)
- Alters protocol-specified study therapy (PD3)
- Impacts the ability of the Sponsor to evaluate the endpoints of the study (PD4)
- Involves administration of prohibited medications (PD5)

The template of summary tables for the protocol deviations is provided in Appendix 6. Individual subjects with these protocol deviations will be listed with specifics on the deviation.

8. General Analyses Methods

In general, CIT-06 analyses will fall into two categories: analyses for continuous outcome variables and analysis for binary outcome variables.

8.1 Analysis of continuous outcome variables

Continuous scale variables will be displayed as mean, standard deviation, median, minimum and maximum. The Shapiro-Wilk test (Shapiro & Wilk, 1965) will be used to test the normality of this continuous variable. If the hypothesis of normally distributed data is not rejected at the 0.05 significance level, the usual normal 95% confidence interval $\bar{x} \pm t_{0.025}^{n-1} \times \frac{s_x}{\sqrt{n}}$ will be constructed

for the true mean μ . If the data are not normally distributed, the transformations

$y = f(x) = \log x, \sqrt{x}$ and $1/x$ of these variables will be examined sequentially until we fail to reject the hypothesis of normality using the Shapiro-Wilk test at the 0.05 significance level. If a transformation is identified such that normality holds then the sample mean \bar{y} and sample standard deviation s_y will be calculated for the transformed variable. The 95% confidence interval will be constructed as

$$\left[f^{-1} \left(\bar{y} - t_{0.025}^{(n-2)} \frac{s_y}{\sqrt{n}} \right), f^{-1} \left(\bar{y} + t_{0.025}^{(n-2)} \frac{s_y}{\sqrt{n}} \right) \right].$$

If these transformations fail to achieve normality, the bootstrap method will be adopted. One thousand bootstrap samples from the original data set with replacement are obtained. For each bootstrap sample, the sample mean is calculated. The 2.5 and 97.5 percentiles, $p_{0.025}$ and $p_{0.975}$, will be identified from the 1000 bootstrap sample means. The interval $[p_{0.025}, p_{0.975}]$ will be reported as the bootstrap 95% confidence interval for the true mean.

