8.2 Analysis of binary outcome variables

Binary outcome variables will be displayed as percents with 95% exact confidence intervals (Rosner, 1995). The exact confidence interval (P_L, P_U) will be as the solutions to the following equations. If x is the observed outcome (that is, there are x successes in the 24 subjects) then the lower bound will be the solution P_L to the equation

$$0.025 = \Pr \{ \text{at least } x \text{ successes} \mid \text{probability of success} = p_L \} = \sum_{k=x}^{24} \binom{24}{k} p_L^k (1-p_L)^{24-k}.$$

The upper bound will be the solution to the equation

$$0.025 = \Pr \{ \text{no more than } x \text{ successes} \mid \text{probability of success} = p_U \} = \sum_{k=0}^x \binom{24}{x} p_U^k (1 - p_U)^{24-k}.$$

Standard search methods will be used to solve these equations.

8.3 *Analysis of time to event measures*

All time to event measures will be summarized using Kaplan-Meier (product limit) life table methods. Results will be displayed as survival plots. Tables with estimates and 95% confidence intervals for the rates at 1-year, 2-years, and 3-years after the first and last islet transplants will be provided. Separate analyses will be performed for time from first transplant and time from last transplant.

9. Analysis of Demographic and Baseline Measures

9.1 *Baseline Data*

Baseline data collected for the ITT analysis consists of demographic information and medical/physical assessments during the waiting period for islet transplant. These data will be grouped into the following categories:

- Demographic variables
 - Age
 - Sex
 - Race (White, Black, Hispanic, Asian and Other)
- Body Habitus and Quality of Life
 - Body Weight
 - Height
 - Body Mass Index (BMI)
- Diabetes Control
 - Insulin requirement (units/day)
 - HbA1c
 - Fasting and post prandial plasma glucose
 - Fasting and post prandial C-peptide
 - 90-minute C-peptide following consumption of Boost[®] or equivalent
 - 90-minute glucose following consumption of Boost[®] or equivalent
 - Number of severe hypoglycemic events in the last year
 - MAGE score
 - LI
 - Clarke Score
 - HYPO score
 - β -score
 - C-peptide/(glucose·creatinine) ratio

Statistical Analysis Plan

- Measures of Cardiovascular function
 - Carotid intimal thickness
 - Atherogenic profile (fasting lipids, c-reactive protein, serum amyloid A, Apolipoprotein A1, Apolipoprotein B, and the ratio of Apolipoprotein A1 and Apolipoprotein B).
- Measures of Renal function
 - Serum Creatinine

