11.5 Ryan hypoglycemia severity (HYPO) score

The HYPO score involves subject recording of blood glucose readings and hypoglycemic events (BG <3.0 mmol/L [54 mg/dL]) over a 4-week period and recall of all severe hypoglycemic episodes in the previous 12 months. The HYPO score is a scalar quantity based on the severity of hypoglycemic events over a four week period. A hypoglycemic event occurs when a blood sugar reading is less than 54 mg/dL and a series of self-reported questionnaire items determine the severity. The HYPO score is the sum of points awarded to each hypoglycemic event, where a large HYPO score indicates more severity (Ryan, Shandro, K, & al., 2004).

A HYPO score greater than or equal to the 90th percentile (1047) of values derived from an unselected group of type 1 diabetic subjects indicates severe problems with hypoglycemia

The analysis of the raw HYPO score adopts the method for continuous scale variable. Change from baseline will also be calculated and analyzed using the same method.

Subjects with HYPO scores greater than or equal to 1047 will be classified as having severe problems with hypoglycemia, and the analysis of the true rate of this event adopts the method for binary outcome variables.

Statistical Analysis Plan

11.6 *Clarke Score*

The Clarke survey (Clarke, Cox, Julian, Schlundt, & Polonsky, 1995) provides a total score between 0 and 7 (most severe), where scores of 4 or more indicate reduced awareness of hypoglycemia and increased risk of severe hypoglycemic events.

The analysis will treat this variable as continuous and adopts the method for a continuous variable. Change from baseline will also be calculated and analyzed using the same method. The subject will be considered to have reduced awareness if the score is greater than or equal to 4. The rate of reduced awareness will be analyzed using the method for a binary outcome variable.

11.7 *Basal (fasting) and 90-min glucose and C-peptide derived from the mixed-meal tolerance test*

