17.7 Appendix 7 - Summary of Excluded Subjects

Centers	Number of excluded subjects	Reason for exclusion* (n)	# of excluded / (# of excluded + # of included)
University of Alberta			
University of Miami			
University of Minnesota			
University of Pennsylvania			
Emory University			
Northwestern University			
University of California San Francisco			
University of Illinois Chicago			
Massachusetts General Hospital			

* From list of 29 possible reasons.

Statistical Analysis Plan

17.8 Appendix 8 – Analysis Templates for the Secondary Efficacy Endpoints Measured at 75±5 Days Following the First and Last Infusion

	Center									
	Univ of Alberta	Univ of Miami	Univ of Minnesota	Univ of Pennsylvania	Emory Univ	Northwestern Univ	Univ of California San Francisco	Univ of Illinois Chicago	Massachusetts General Hospital	Total
Continuous Outcomes										
Insulin Req.										
n										
mean										
s.d.										
median										
range										
95% CI of mean										
HbA1c										
n										
mean										
s.d.										
median										
range										
95% CI of mean										
MAGE										

Statistical Analysis Plan

n mean s.d. median range 95% CI of mean										
LI n mean s.d. median range 95% CI of mean										
Hypo n mean s.d. median range 95% CI of mean										
Glucose Change n mean s.d. median										

Statistical Analysis Plan

range 95% CI of mean										
β-score n mean s.d. median range 95% CI of mean										
C- pep:glucose ratio n mean s.d. median range 95% CI of mean										
AIRglu n mean s.d. median range 95% CI of mean										

Statistical Analysis Plan

SI n mean s.d. median range 95% CI of mean										
DI n mean s.d. median range 95% CI of mean										
Glucose variability n mean s.d. median range 95% CI of mean										

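### Section 8.1 back-transforms limits from the log, square-root or 1/x scale and reports them as a CI of the mean, so intervals for skewed secondary endpoints lie too low

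*SAP*

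**What the plan says.** SAP Section 8.1 has three branches.

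1. If Shapiro-Wilk does not reject normality, a t interval with n−1 df is given for the true mean.
2. If it rejects, the log, square-root and reciprocal scales are tried in that order. The stopping rule is that the transforms "of these variables will be examined sequentially until we fail to reject the hypothesis of normality using the Shapiro-Wilk test at the 0.05 significance level". Once a scale has been accepted, the wording runs "If a transformation is identified such that normality holds then the sample mean", and this mean, like the SD, belongs to the transformed variable y. "The 95% confidence interval will be constructed as" introduces limits formed on the y scale with t on n−2 df and passed through the inverse function. No parameter is named and nothing converts the limits back to the mean of x.
3. If no transformation works, percentile limits from 1,000 bootstrap means "will be reported as the bootstrap 95% confidence interval for the true mean".

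The data display in Section 8.1 is the arithmetic mean, SD, median, minimum and maximum. In the Appendix 8 template the row for HYPO reads "Hypo n mean s.d. median range 95% CI of mean". The row for the lability index has the same form: "LI n mean s.d. median range 95% CI of mean". Appendix 9 uses the same label. Sections 12.3.2 to 12.3.4 also describe the output of this method as a CI of the mean. Sections 11.4 and 11.5 send LI and HYPO to it. Section 11.5 adds: "Change from baseline will also be calculated and analyzed using the same method".

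**The concern.** The outer two branches estimate the arithmetic mean and the middle one does not, yet all three feed the same table row. Back-transformed limits bound exp(E[log x]), (E[√x])² or 1/E[1/x]. For right-skewed data each of these lies below E[x]. A reader of the final tables would see a mean with an interval that is too low and may not contain that mean.

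The branch is chosen by a test on each data set. The same endpoint can therefore change parameter between visits, or between the first-transplant and last-transplant analyses, which makes the intervals hard to compare over time.

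Three lesser faults sit in the same formula. With 1/x the printed lower limit exceeds the upper. The df are n−2 where a one-sample mean has n−1. No rule covers zeros (log and 1/x undefined) or negative change scores (log and √ undefined).

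**Working it through.** **Inputs.** n = 24 (Section 4). Table 4.4 mean/SD: HYPO 850/750, LI 223/200, MAGE 8/4, HbA1c 6/0.7. Section 11.4 for LI: median 223, quartiles 130 and 329, 90th percentile 433. The SAP gives no distribution shape. Lognormal and gamma are assumptions.

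**The plan's own precision figure.** Half-width = 1.96 × SD/√24 = 0.400 × SD. HYPO: 0.400 × 750 = 300. LI: 0.400 × 200 = 80. Both match Table 4.4, which confirms that the planned precision refers to the arithmetic mean with 24 subjects.

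**Size of the shift, lognormal data.** σ² = ln(1 + (SD/mean)²) and geometric mean = mean/√(1 + (SD/mean)²).
- HYPO: σ² = ln(1.779) = 0.576, σ = 0.76; geometric mean 850/1.334 = 637.
- LI: σ² = ln(1.804) = 0.590, σ = 0.77; geometric mean 223/1.343 = 166.

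The back-transformed interval is thus centred at about 0.75 of the mean.

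**Hand check of the log branch.** On the log scale the true mean lies σ²/2 above the centre and the standard error is σ/√n, so the offset is σ√n/2 standard errors. For HYPO this is 0.759 × 4.899/2 = 1.86, against a critical value of 2.074 (22 df). Coverage is roughly Φ(2.074 − 1.86) = Φ(0.21) ≈ 0.58. Simulating the log interval alone gives 0.57.

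**Full Section 8.1 procedure, simulated at n = 24** (Shapiro-Wilk on x, then log, √, 1/x, then bootstrap; several thousand samples per scenario; nominal miss rate 5%):

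| Endpoint and input | Misses the true mean |
|---|---|
| HYPO, lognormal / gamma | 39.8% / 37.7% |
| LI, lognormal / gamma | 41.4% / 39.9% |
| LI, lognormal from Section 11.4: 90th percentile / quartile range / lower quartile | 17% / 34% / 45% |
| MAGE, both shapes | about 11–17% |
| HbA1c, both shapes | about 5–6% |
| HYPO with 10% zeros (assumed) | about 18% (15% in one run) |
| HYPO with 30% zeros (assumed) | about 6% |

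For HYPO and LI at the Table 4.4 values, a transformation is used in 82–87% of samples and nearly all misses fall below the mean. In 14–27% of samples the interval excludes the sample mean printed beside it. In the zero scenarios, undefined transformations are skipped and the overall mean and SD are held at 850 and 750. With 30% zeros about three quarters of samples reach the bootstrap, which does target the mean.

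**Alternatives on the same lognormal data (HYPO, LI).** Plain t covers 91.2% and 90.3%. The percentile bootstrap covers 89.8% and 88.9%. Cox's interval for a lognormal mean covers 94.8% and 94.7%. The log-branch interval covers the geometric mean about 95% of the time, so it is a sound interval with the wrong label.

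**Degrees of freedom.** t is 2.074 on 22 df and 2.069 on 23 df, a negligible difference.

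**The case against.** Several points on the other side stand.

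- **Shape and zeros.** A reader might take 40% as a fixed property of these endpoints. The SAP does not support that. HYPO sums points over hypoglycemic events, so zeros after transplant are plausible, and the miss rate then falls sharply. The two sources for LI also disagree: 223 is a mean in Table 4.4 and a median in Section 11.4.
- **Reach.** A reader might infer that these intervals carry all the inference on metabolic and quality-of-life outcomes. They do not. Quality-of-life scores also have mixed models (Section 12.3), many metabolic outcomes have mixed-model change analyses (Section 13), and MAGE, LI, HYPO and Clarke have binary analyses (Sections 11.3 to 11.6). Medians are shown as well. Section 10.2 calls the secondary analyses descriptive. HbA1c keeps the ordinary t interval in over 90% of simulated samples.
- **Change scores.** Negative values rule out log and √. On a natural reading such data stay with the t interval or go to the bootstrap, and both target the mean. What is missing is an explicit rule.
- **Binomial formulas.** A reader might also infer wrong binomial limits or a wrong primary decision. In Section 8.2, "The upper bound will be the solution to the equation" leads to a sum printed with C(24,x) where C(24,k) is meant. The words in that equation define the bound correctly and the lower-limit sum is right, so this is a misprint. The fixed 24 in Sections 8.2 and 10.1 is the planned number. The Section 10.1 decision rests on an exact test that is not tied to 24. Only the bound reported with it would be off, and only if the ITT count differed and the formula were run literally.

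Back-transforming to a geometric mean is also common practice. None of this removes the fault, because the SAP nowhere calls the result a geometric mean and its templates call it a CI of the mean.

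**Conclusion.** The point holds in a limited form. The transformed branch of Section 8.1 produces an interval for a different parameter from the one its label names. For strictly positive, clearly skewed data at the Table 4.4 values, the miss rate is about 38–41% for HYPO and LI instead of 5%, and the intervals lie too low. These figures rest on assumed lognormal or gamma shapes without zeros. The effect is moderate for MAGE, near nil for HbA1c, and shrinks for HYPO as zeros become common. What is at stake is the correctness and comparability of descriptive CIs for skewed continuous secondary endpoints. The conclusion on the primary endpoint does not depend on it. The change should be made before analysis, since it is cheap and the text as written would be programmed literally.

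**What to change.** In Section 8.1:

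- Choose the scale once per endpoint, in advance, instead of by a Shapiro-Wilk test at each visit.
- Then take one of two routes. (a) Report an interval that targets the mean: t with n−1 df or the bootstrap, stating that coverage is about 89–93% on data this skewed, or a lognormal-mean interval such as Cox's (about 95% if the data are lognormal). (b) For strictly positive variables keep the log interval with n−1 df, report the geometric mean, and label the CI so in Appendices 8 and 9.
- Use the untransformed or bootstrap interval for variables that can be zero and for all change scores, and say so.
- If 1/x is kept, put the limits in the right order and name the parameter.

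Editorial: print C(n,k) in the Section 8.2 upper-limit sum, and use the actual ITT n in place of 24 in Sections 8.2 and 10.1.

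Cost: SAP wording, table labels and programming. Some intervals will be wider. No data collection or sample size changes.
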